## 1 PROTOCOL SUMMARY

### 1.1 Synopsis

Name of Sponsor/Company: I-Mab Biopharma US Limited
Title of Study: A PHASE 2 CLINICAL STUDY OF TJ004309 IN COMBINATION WITH ATEZOLIZUMAB (TECENTRIQ®) IN PATIENTS WITH ADVANCED OR METASTATIC OVARIAN CANCERS AND SELECTED ADVANCED SOLID TUMORS
Name of Investigational Product: TJ004309
Principal Investigators: To be determined


of PD-L1 and CD73 with responses. This clinical study is designed to evaluate the efficacy and safety of TJ004309 combination therapy in patients with ovarian cancers and selected advanced solid tumors.

### **Objectives:**

The primary objectives of the study are:

- Part 1: To assess the efficacy of TJ004309 combined with atezolizumab in a cohort of patients with platinum-resistant IO naïve ovarian carcinoma and a separate biomarker enriched cohort of subjects with selected tumor types
- Part 2: To further evaluate and confirm the efficacy in targeted patient population based on the efficacy observed in Part 1

The secondary objectives of the study are:

- To evaluate the safety and tolerability of TJ004309 when combined with the standard dose of atezolizumab
- Part 1: To characterize the pharmacokinetic profile of TJ004309 when administered in combination with atezolizumab
- Part 1: To determine the immunogenicity of TJ004309 when administered in combination with atezolizumab

The exploratory objectives of the study are:

- To investigate the expression of PD-L1, CD73, and other immune subset markers (CD8, CD68, CD19 and CD163) in tumor biopsies at baseline and on treatment, and their associations with clinical responses
- To examine the CD73 enzymatic activity of tumor biopsies
- To study the whole genome gene expression profiles in tumor biopsies

### **Study design:**

This is a multicenter, open label, Phase 2 study of TJ004309 in combination with atezolizumab in patients with advanced or metastatic solid tumors. This clinical study will be conducted in two parts. Part 1 of the study will include two cohorts: Cohort 1 will include Immuno-Oncology (IO) treatment naïve ovarian cancer (OC) patients who have progressed on or after platinum therapy; and Cohort 2 will include patients with head and neck squamous cell carcinoma (HNSCC), non-small cell lung cancer (NSCLC), gastrointestinal cancer (GC), triple negative breast cancer (TNBC), or ovarian carcinoma (OC) with PD-L1 expression  $\geq 1\%$  (Table 1). All subjects will be evaluated for antitumor activity on a regular basis as specified in the protocol and their clinical status classified according to RECIST 1.1 and iRECIST. Treatments may continue until clinically significant disease progression, unacceptable toxicity, or subject/Investigator decision to withdraw. Based on the efficacy observation in Part 1, Part 2 of the study will further evaluate the efficacy in selected targeted patient populations and will be initiated after reaching agreement with the regulatory agency.

TJ004309 will be given in combination with atezolizumab 1200 mg every 3 weeks (Q3W) beginning with Cycle 1 Day 1 (C1D1). Premedication will be given prior to the initial infusion of TJ004309 to mitigate infusion related reactions. Each cycle will be 21 days in duration.

**Table 1: Study Drug Dosing Schedule – Part 1**

Cohort	TJ004309 Q3W	Atezolizumab Q3W	Subjects
Cohort 1: Platinum resistant or refractory IO naïve ovarian carcinoma (OC)	20 mg/kg	1200 mg flat dose	N= 30
Cohort 2: HNSCC, NSCLC, GC, TNBC, OC	20 mg/kg	1200 mg flat dose	N= 30

Up to 30 subjects will be enrolled in each cohort. If two or less responses are observed from the first 15 subjects in Cohort 1, the enrollment may be stopped based on rules from a Simon's 2-stage design. If 3 or more responses are observed from the first 15 subjects in Cohort 1 from Part 1, then Part 2 of the study may be initiated earlier. If any response is observed from Cohort 2, an additional cohort with up to 30 subjects may be opened with a specific tumor type after reviewing all other available data at that time.

#### **Safety Follow-up Period**

After the treatment periods, all subjects will enter a safety follow-up period and will be evaluated for safety, tolerability, and tumor response (if applicable) for at least 90 days after the last dose of study drug, or 30 days following cessation of study treatment if the subject initiates new anticancer therapy, whichever is earlier. Subjects will be required to return to the study sites for three (3) safety follow-up visits (approximately 30, 60 and 90 days after the last dose of study drug), except those subjects who withdraw consent for study participation. After treatment discontinuation, in the event of continuing serious adverse events (SAEs), subjects will be followed until resolution or stabilization of the SAEs (regardless of the relationship to the IMP). Any subject who has an ongoing non-serious AE that is possibly related or related to the IMP or study procedures at the 90-day post-treatment Follow-up visit will be followed up, where possible, until resolution or until the unresolved non-serious AE is judged by the Investigator (or designee) to have stabilized. Any subject who has an ongoing non-serious AE that is not related or unlikely related to the IMP or study procedures at the Follow-up visit, can be closed out as ongoing at the Investigator's discretion. If a subject initiates a new anticancer therapy within 30 days after the last dose of study treatment, one (1) Post-Treatment Safety Follow-Up visit should occur approximately 30 days after the last dose of study drug and therefore subsequent follow-up visits will not be required.

#### **Response/Survival Follow-up Period**

Subjects who do not experience progressive disease prior to treatment discontinuation will continue to have radiologic and clinical tumor assessments every 9 weeks for the first year and every 12 weeks during the second year until progression is confirmed, consent withdrawal, start of a new anti-cancer treatment, loss to follow-up, or death, whichever comes first. These subjects will also be followed by telephone every 12 weeks during the second year. The duration for response/survival follow-up is approximately 2 years from the first dose of study drug.

**Diagnosis and Main Criteria for Inclusion:**
**Inclusion Criteria:**

1. Males or females, age  $\geq$  18 years
2. Eastern Cooperative Oncology Group (ECOG) performance status  $\leq$  1
3. In all cohorts, archival tumor tissue in a tissue block or biopsy specimen that allows the preparation of at least 20 slides prior to study entry. Tissue blocks are preferred. Archival tumor tissue is acceptable in either format per site's preference.
4. Cohort 1 - Ovarian Carcinoma (OC):
  - a. Histologically confirmed epithelial ovarian cancer, fallopian tube, or primary peritoneal cancer subjects with any high-grade serous component, progressed on or after platinum-containing therapy and not eligible for further platinum containing treatment (platinum-resistant, platinum-refractory disease defined by progression of disease on a platinum-containing regimen or recurrence of disease within 180 days of receiving the last dose of platinum-based treatment).
  - b. Prior lines of therapy to include:
    - Patients must have had 1 to 3 prior lines of therapy including at least one bevacizumab-containing regimen or ineligible for all other available therapies; Or
    - Patients must be in the 4th or 5th line of treatment, irrespective of bevacizumab or who are ineligible for all therapies with demonstrated clinical benefit; Or
    - Patients with known BRCA-positive associated cancer or mutation, prior therapy must include PARP inhibitors (unless contraindicated)
5. Cohort 2 - Patients with selected tumor types that have relapsed or progressed after 2 lines of therapy or who are ineligible for other standard of care (SOC) therapies:
  - a. Histologically or cytologically confirmed metastatic NSCLC
  - b. Histologically or cytologically confirmed recurrent or metastatic HNSCC (oral cavity, oropharynx, hypopharynx, or larynx)
  - c. Histologically or cytologically confirmed metastatic or non-resectable advanced metastatic gastric or gastroesophageal adenocarcinoma
  - d. Histologically or cytologically confirmed unresectable, locally advanced or metastatic TNBC (confirmed HER2-negative, estrogen receptor-negative and progesterone receptor-negative)
  - e. Histologically confirmed ovarian cancer of all high-grade epithelial types who are IO treatment naïve and have progressed after 3 months on or after platinum-containing therapy
  - f. PD-L1 expression Tumor Proportion Score (TPS)  $\geq$  1% for NSCLC and Combined Proportion Score (CPS)  $\geq$  1% for all other tumor types
  - g. A 28-day washout period after the completion of programmed death-1 (PD-1)/PD-L1 therapy
  - h. Patients should have no more than 5 prior lines of therapies
  - i. If the patients have progressed on treatment with prior PD-1/L1 inhibitor administered either as monotherapy or in combination with other therapies, additional following criteria must be met:

- have received at least 2 doses of the PD-1/L1 inhibitor;
- have been on a continuous regimen of the PD-1/L1 inhibitor for at least 4 months without disease progression;
- have demonstrated radiographic disease progression after PD-1/L1

j. Patients who have had more than 1 prior PD-1/L1 inhibitor may be considered after discussion with the Sponsor's Medical Monitor

6. Cohort 2 - Pre-treatment fresh tumor biopsies and paired treatment fresh tumor biopsies will be collected from at least 5 patients. Biopsy must be excisional, incisional, or core. Fine needle aspiration is insufficient. Waiver of biopsy samples must be discussed with Sponsor's Medical Monitor. NOTE: CD73 enzymatic activity and assessment of proteins in the adenosine pathway (e.g., CD73, A2A receptor, and whole genome gene expression profiles) will be assessed in fresh tumor biopsies. Samples will be collected prior to dosing and processed and shipped within 24 hours according to a separate laboratory manual. The fresh tumor biopsies require testing for the following infectious diseases: Hepatitis B, Hepatitis C, Tuberculosis, HIV, Syphilis, and COVID-19. Testing must be completed within 28 days of tumor biopsy collection and confirmed to be negative.

7. Willingness and ability to consent for self to participate in study and the ability to comply with scheduled visits, treatment plan, laboratory tests, and other study procedures

8. Patients who received prior PD-1/PD-L1 checkpoint inhibitor or prior CTLA-4 inhibitor therapy may enroll to Cohort 2 if they did not experience Grade 3 immune-related toxicity (applies to all tumor types except ovarian cancer patients)

9. At least one measurable lesion as defined by RECIST 1.1

10. Resolution of all acute adverse events resulting from prior cancer therapies to National Cancer Institute (NCI) Common Terminology Criteria for Adverse Events (CTCAE) v5.0 Grade  $\leq$  1 or baseline (except alopecia or neuropathy)

11. Considered by the Investigator to be an appropriate candidate for a clinical study, with a life expectancy of  $\geq$  12 weeks

12. Adequate organ function as defined by the following criteria:

- a. Absolute neutrophil count (ANC)  $\geq$  1500/ $\mu$ L
- b. Platelets  $\geq$  100,000/ $\mu$ L without transfusion support within 28 days prior to study treatment
- c. Hemoglobin  $\geq$  9.0 g/dL without transfusion support within 7 days prior to study treatment (erythropoietin or darbepoetin permitted)
- d. Creatinine clearance  $>$  30 mL/min by Cockcroft-Gault formula
- e. Serum aspartate transaminase (AST; serum glutamic oxaloacetic transaminase [SGOT]) and serum alanine transaminase (ALT; serum glutamic pyruvic transaminase [SGPT])  $\leq$  3 times upper limit of normal (ULN) or  $\leq$  5 times ULN in cases of liver metastases
- f. Total serum bilirubin  $\leq$  1.5 times the ULN, unless patient has documented Gilbert's disease in which case bilirubin  $\leq$  3.0 times the ULN
- g. International normalized ratio (INR) from 0.8 to 1.2 unless the INR elevation is related to use of a Factor Xa Inhibitor

- h. Activated partial thromboplastin time (aPTT)  $\leq 1.5 \times$  ULN unless patient is receiving anticoagulant therapy if PT or PTT is within therapeutic range of intended use of anticoagulants
- 13. No systemic anti-cancer therapy within 4 weeks of starting study treatment or at least 5 half-lives (whichever is shorter) before study drug administration, and all AEs have either resolved or stabilized. Note: Participants who have entered the follow-up phase of an investigational study may participate if it has been 4 weeks after the last dose of the previous investigational agent.
- 14. Subject with a QT interval corrected for heart rate using Fridericia's formula (QTcF) and/or QT interval corrected for heart rate using Bazett's formula of  $\leq 480$  msec. NOTE: If a patient has a prolonged QT interval and the prolongation is deemed to be due to a pacemaker upon Investigator evaluation (i.e., the patient otherwise has no cardiac abnormalities), the patient may be eligible to participate in the study following discussion with the Sponsor's Medical Monitor.
- 15. Women of childbearing potential (WOCBP) must:
  - a. Agree to use at least 2 effective contraceptive methods (1 highly effective method in combination with a barrier method; oral, injectable, or implantable hormonal contraceptive; tubal ligation; intra-uterine device; barrier contraceptive with spermicide; or vasectomized partner), one of which must be barrier. Use of contraceptive methods lasts from date of ICF signature, throughout the study, and for up to 5 months following the last dose of TJ004309.
  - b. Have a negative serum pregnancy test (sensitive of at least 25 mIU/ml) at Screening; and have a negative serum or urine pregnancy test within 72 hours prior to Cycle 1 Day 1 of study treatment (note that the screening serum pregnancy test can be used as the test prior to Day 1 study treatment if it is performed within the prior 72 hours)
  - c. Avoid conceiving for 5 months after the last dose of TJ004309
  - d. Avoid donation of ova from date of ICF signature until 5 months after the last dose of TJ004309
  - e. Agree to ongoing urine pregnancy testing, if clinically indicated, during the study
- 16. Males must agree to use a condom (a latex condom is recommended) during sexual contact with a pregnant female or a female of childbearing potential, will avoid donation of sperm, or having a female partner conceive from date of ICF signature, while participating in the study, during dose interruptions, and for at least 5 months after the last dose of study treatment, even if he has undergone a successful vasectomy.

Exclusion Criteria:

- 1. Autoimmune disease requiring active treatment within the past twelve months (Note: vitiligo, type 1 diabetes mellitus, residual hypothyroidism due to autoimmune thyroiditis only requiring hormone replacement, and conditions not expected to recur in the absence of an external trigger are permitted)
- 2. Condition requiring systemic treatment with either corticosteroids ( $>10$  mg daily prednisone equivalent) or other immunosuppressive medications within 14 days prior to study treatment

(Note: inhaled and topical steroids, and adrenal replacement steroid doses > 10 mg daily prednisone equivalent, are permitted in the absence of active autoimmune disease.)

3. Has a history of (non-infectious) pneumonitis/interstitial lung disease that required steroids or has current pneumonitis/interstitial lung disease
4. Current treatment on another therapeutic clinical trial
5. Has received prior therapy with an anti-PD-1, anti-PD-L1, or anti-PD-L2 agent or with an agent directed to another stimulatory or co-inhibitory T-cell receptor (e.g. cytotoxic T-lymphocyte-associated protein 4 [CTLA-4], OX 40 [Tumor necrosis factor receptor superfamily, member 4 (TNFRSF4)], CD137 [tumor necrosis factor receptor superfamily member 9 (TNFRSF9)]) (only applies to ovarian cancer patients in Cohorts 1 and 2)
6. For ovarian patients in both cohorts:
  - a. Patients who progressed during or within 3 months of first line of platinum-based therapy
  - b. Patients with histologically non-epithelial tumors or ovarian tumors with low malignant potential (i.e., borderline tumors) or mucinous tumors
  - c. Patients with evidence of bowel obstruction requiring hospitalization and decompression within the past 30 days
7. Major surgical procedure or significant traumatic injury within 4 weeks prior to study treatment, and must have fully recovered from any such procedure; and no date of surgery (if applicable) or anticipated need for a major surgical procedure planned within the next 6 months (The following situations are not considered to be major procedures and are permitted up to 7 days prior to study treatment: thoracentesis, paracentesis, port placement, laparoscopy, thoracoscopy, tube thoracostomy, bronchoscopy, endoscopic ultrasonographic procedures, mediastinoscopy, incisional biopsies, and routine dental procedures. Core biopsy and skin biopsy do not require a waiting period prior to dosing.)
8. Chest radiotherapy  $\leq$  28 days, wide field radiotherapy  $\leq$  28 days (defined as > 50% of volume of pelvic bones or equivalent), or limited field radiation for palliation  $\leq$  14 days prior to study treatment
9. Pleural effusion or ascites that requires therapeutic paracentesis in the last 30 days
10. Brain involvement with cancer, spinal cord compression, carcinomatous meningitis, or new evidence of brain or leptomeningeal disease; unless the lesion(s) have been radiated or resected, are considered fully treated and inactive, are asymptomatic, and no steroids have been administered for CNS disease over the 7 days prior to study treatment
11. Angina, myocardial infarction (MI), symptomatic congestive heart failure, cerebrovascular accident, transient ischemic attack TIA), arterial embolism, pulmonary embolism, percutaneous transluminal coronary angioplasty (PTCA), or coronary artery bypass grafting (CABG) within 6 months prior to study treatment
12. Thrombolytic use (except to maintain IV catheters) within 10 days prior study treatment
13. Known active or chronic Hepatitis B or Hepatitis C, other hepatitides (non-alcohol steatohepatitis, alcohol or drug-related, autoimmune) serology at screening or cirrhosis

14. Any active infection requiring parenteral treatment
15. History of hemorrhage or hemoptysis (> ½ teaspoon bright red blood) within 3 months prior to study treatment
16. Known human immunodeficiency virus (HIV) unless CD4+ T cell count > 350 cells/ $\mu$ L with an undetectable viral load
17. Pregnancy or breastfeeding - Female patients must be surgically sterile (i.e.,  $\geq$  6 weeks following surgical bilateral oophorectomy with or without hysterectomy or tubal ligation) or be postmenopausal for at least one year or must agree to use effective contraception during the study and for 5 months following last dose of TJ004309. All female patients of reproductive potential must have a negative pregnancy test (serum or urine) within 72 hours prior to study treatment. Male patients must be surgically sterile or must agree to use effective contraception during the study and for 5 months following last dose of TJ004309
18. Patients with any severe infection within 4 weeks prior to initiation of study treatment, including, but not limited to, hospitalization for complications of infections should not be enrolled in the trial. Patients who required IV antibiotics or were treated with antiviral medications within this 4 week period should be discussed with the Sponsor Medical Monitor prior to enrollment
19. Other severe acute or chronic medical or psychiatric condition or laboratory abnormality that may increase the risk associated with study participation or may interfere with the interpretation of study results and, in the judgment of the Investigator, would make the patient inappropriate for this study

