- t) Dipstick is acceptable. Microscopic analyses if dipstick is abnormal. No need to repeat on Cycle 1 Day 1 if screening assessment performed within 72 hours prior to that date. If  $\geq 2+$  protein on urine dipstick, then collect spot urine sample to calculate urine protein to creatinine ratio.
- u) Tumor assessments will be performed at Screening, Cycle 4 Day 1, then every 9 weeks for 1 year following the first dose of study drug, and every 12 weeks for the second year. Scans within 28 days of Cycle 1 Day 1, prior to signing the ICF, can be used as the screening scan. On-treatment scans can be obtained  $\pm 7$  days. The same modality (CT, PET/CT or MRI) should be used throughout the study for a given patient. Collection of images will be obtained for retrospective analysis. Central review of scans may be performed during the study.

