11. Considered by the Investigator to be an appropriate candidate for a clinical study, with a life expectancy of  $\geq 12$  weeks

12. Adequate organ function as defined by the following criteria:

- a. Absolute neutrophil count (ANC)  $\geq 1500/\mu\text{L}$
- b. Platelets  $\geq 100,000/\mu\text{L}$  without transfusion support within 28 days prior to study treatment
- c. Hemoglobin  $\geq 9.0 \text{ g/dL}$  without transfusion support within 7 days prior to study treatment (erythropoietin or darbepoetin permitted)
- d. Creatinine clearance  $> 30 \text{ mL/min}$  by Cockcroft-Gault formula

- e. Serum aspartate transaminase (AST; serum glutamic oxaloacetic transaminase [SGOT]) and serum alanine transaminase (ALT; serum glutamic pyruvic transaminase [SGPT])  $\leq$  3 times upper limit of normal (ULN) or  $\leq$  5 times ULN in cases of liver metastases
- f. Total serum bilirubin  $\leq$  1.5 times the ULN, unless patient has documented Gilbert's disease in which case bilirubin  $\leq$  3.0 times the ULN
- g. International normalized ratio (INR) from 0.8 to 1.2 unless the INR elevation is related to use of a Factor Xa Inhibitor
- h. Activated partial thromboplastin time (aPTT)  $\leq$  1.5 $\times$  ULN unless patient is receiving anticoagulant therapy if PT or PTT is within therapeutic range of intended use of anticoagulants

13. No systemic anti-cancer therapy within 4 weeks of starting study treatment or at least 5 half-lives (whichever is shorter) before study drug administration, and all AEs have either resolved or stabilized. Note: Participants who have entered the follow-up phase of an investigational study may participate if it has been 4 weeks after the last dose of the previous investigational agent.

14. Subject with a QT interval corrected for heart rate using Fridericia's formula (QTcF) and/or QT interval corrected for heart rate using Bazett's formula of  $\leq$  480 msec. NOTE: If a patient has a prolonged QT interval and the prolongation is deemed to be due to a pacemaker upon Investigator evaluation (i.e., the patient otherwise has no cardiac abnormalities), the patient may be eligible to participate in the study following discussion with the Sponsor's Medical Monitor.

15. Women of childbearing potential (WOCBP) must:

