**Non-target lesions**

All other lesions (or sites of disease) including pathological lymph nodes (with short axis  $\geq 10$  mm and  $< 15$  mm) should be identified as non-target lesions and should also be recorded at baseline. Measurements are not required and these lesions should be followed as ‘present,’ ‘absent,’ or in rare cases ‘unequivocal progression’ (more details to follow). In addition, it is possible to record multiple non-target lesions involving the same organ as a single item on the Case Report Form (e.g., ‘multiple enlarged pelvic lymph nodes’ or ‘multiple liver metastases’).

**Response Criteria:** The BOR is the best response recorded from the start of the study treatment until the end of treatment. The subject’s BOR assignment will depend on the findings of both target and non-target disease and will also take into consideration the appearance of new lesions.

**Complete Response (CR):** Disappearance of all target lesions. Any pathological lymph nodes (whether target or non-target) must have decreased in size to have a short axis of  $< 10$  mm.

**Partial Response (PR):** At least a 30% decrease in the sum of diameters of target lesions taking as reference the baseline sum diameters.

**Stable Disease (SD):** Neither sufficient shrinkage to qualify for PR nor sufficient increase to qualify for progressive disease (PD), taking as reference the smallest sum diameters while on study.

**Non-CR/Non-PD:** Persistence of one or more non-target lesion(s) and/or maintenance of tumor marker level above the normal limits.

**Progressive Disease (PD):** At least a 20% increase in the sum of diameters of target lesions, taking as reference the smallest sum on study (this includes the baseline sum if that is the smallest on study). In addition to the relative increase of 20%, the sum must also demonstrate an absolute increase of at least 5 mm. For non-target lesions, unequivocal progression (see comments below) of existing lesions represents PD. Note: the appearance of one or more new lesions is also considered progression.

Lymph nodes identified as target lesions should always have the actual short axis measurement recorded (measured in the same anatomical plane as the baseline examination), even if the nodes regress to below 10 mm on study. This means that when lymph nodes are included as target lesions, the 'sum' of lesions may not be zero even if CR criteria are met, since a normal lymph node is defined as having a short axis of <10 mm.

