4.3 BASELINE AND STUDY DAY DEFINITIONS

4.3.1 Baseline Definition

Baseline is defined as the last non-missing measurement prior to the first dose of study drug. If multiple values are present for the same time point (same date if time is absent,

or same datetime), the average of the non-missing values will be used as the baseline. If there is no non-missing measurement prior to the first dose, the baseline value will not be imputed and will remain missing.

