8.1 BEST OVERALL RESPONSE (BOR) AND OBJECTIVE RESPONSE RATE (ORR) PER RECIST v1.1

Responses to the study treatment are categorized per RECIST 1.1 as the following (from the best to the worst): complete response (CR), partial response (PR), stable disease (SD), progressive disease (PD) and not evaluable (NE).

Per RECIST 1.1, the best overall response (BOR) for a subject is the best response of CR, PR, SD, PD and NE observed from the first dose of study drug until PD or the end of

treatment, whichever occurs earlier. The objective response rate (ORR) is the proportion of subjects whose BOR is either CR or PR.

8.2 iBOR AND iORR PER iRECIST

iRECIST is based on RECIST 1.1 but adapted to account for the unique tumor response seen with immunotherapeutic drugs. iRECIST introduces new criteria of unconfirmed progressive disease (iUPD) and confirmed progressive disease (iCPD) to prevent the discontinuation of study treatment in cases of pseudoprogression. Immune responses assigned by the iRECIST criteria are (from the best to the worst): complete response (iCR), partial response (iPR), stable disease (iSD), unconfirmed progressive disease (iUPD), confirmed progressive disease (iCPD) and not evaluable (NE).

There is no distinct iRECIST assessment until radiographic disease progression based on RECIST 1.1. For participants who show evidence of radiological PD by RECIST 1.1 as determined by the Investigator, the Investigator will decide whether to continue a participant on study treatment until repeat tumor imaging is obtained for confirmation of PD by iRECIST.

Per iRECIST, the best overall response (iBOR) for a subject is the best response of iCR, iPR, iSD, iUPD, iCPD and NE observed from the first dose of study drug until iCPD or the end of treatment, whichever occurs earlier. The objective response rate (iORR) is the proportion of subjects whose iBOR is either iCR or iPR.

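### Inclusion 13 and the 28-day scan window together allow the RECIST baseline to precede the last dose of a short-half-life prior therapy, so tumour change from that drug can enter the ORR

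*Protocol*

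**What the plan says.** **Washout.** Protocol inclusion 13 reads "No systemic anti-cancer therapy within 4 weeks of starting study treatment or at least 5 half-lives (whichever is shorter) before study drug administration". Section 5.1 repeats the rule with the same clause, "or at least 5 half-lives (whichever is shorter) before study drug administration", so it is not a slip in the synopsis. Two groups have a longer washout. For prior checkpoint therapy, Cohort 2 requires "A 28-day washout period after the completion of programmed death-1 (PD-1)/PD-L1 therapy". The note to inclusion 13 requires 4 weeks since the last investigational agent for people in follow-up on another study.

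**Baseline scan.** Table 2 footnote u says "Scans within 28 days of Cycle 1 Day 1, prior to signing the ICF, can be used as the screening scan". It does not mention the last dose of prior therapy.

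**Response.** Protocol Appendix 1 defines PR as "At least a 30% decrease in the sum of diameters of target lesions taking as reference the baseline sum diameters". SAP 4.3.1 states "Baseline is defined as the last non-missing measurement prior to the first dose of study drug". SAP 8.1 takes the best response "observed from the first dose of study drug until PD or the end of" treatment, with no rule for carry-over from earlier treatment. ORR by RECIST 1.1 is the primary endpoint (Protocol 3.2.1), and Part 1 is single-arm (Protocol 6.6).

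**Progression at entry.** Cohort 1 ties progression to platinum, not to the most recent regimen. Cohort 2 takes patients who "have relapsed or progressed after 2 lines of therapy or who are ineligible for other standard of care (SOC) therapies", and the second route does not require progression on the last drug.

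**The concern.** The washout and the scan window match only when the 4-week limit applies. When the half-life limit is the shorter one, prior treatment may continue after the scan that becomes the RECIST reference. Any change the earlier drug causes between that scan and first study dose is then counted as change on study treatment.

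There is no control arm in which the same artefact would appear. SAP section 8 also drops DOR, PFS and OS because the study report is abbreviated. BOR and ORR are therefore the whole efficacy summary, and no durability analysis would help show whether a response belonged to the study drugs. Central review, which footnote u makes optional, would not help either, since it would read against the same baseline scan.

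**Working it through.** The documents give no figure on this point, so there is nothing of the plan's own to reproduce.

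**Step 1: dates.**
- Minimum washout (inclusion 13): W = min(28, 5 × half-life) days.
- Oldest permitted baseline scan (footnote u): 28 days before Cycle 1 Day 1.
- Longest time the scan can precede the last prior dose: 28 − W.
- Break-even half-life: 28 / 5 = 5.6 days.

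The half-lives below are assumptions; the documents give none for prior agents.

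| Assumed half-life (days) | W (days) | 28 − W (days) |
|---|---|---|
| 0.5 | 2.5 | 25.5 |
| 1 | 5 | 23 |
| 2 | 10 | 18 |
| 3 | 15 | 13 |
| 5 | 25 | 3 |
| 5.6 or more | 28 | 0 |

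The overlap comes only from the half-life branch: a full 28-day washout with a 28-day scan window gives zero.

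**Step 2: does another rule close the gap?**
- The PD-1/PD-L1 and investigational-agent washouts close it for those agents only.
- Protocol 6.8.1 bars other anti-cancer therapy during study participation. If participation starts at consent, the overlap needs a pre-consent scan, which footnote u expressly allows.
- The SAP baseline is the last pre-dose measurement, so a later second scan would replace an early one. Nothing requires a second scan.
- Appendix 1 indicates that CR and PR need confirmation in non-randomised trials. Confirmation would use the same baseline, and SAP 8.1 does not restate it.

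**Step 3: effect on one patient.** As a constructed illustration, take a 20% fall between scan and first dose, then 13% on study. The recorded change is 1 − 0.80 × 0.87 = 0.304, or 30.4%, which meets the PR threshold; 13% alone would not.

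**Step 4: effect on the reported rate.** One misattributed response adds 1/15 = 6.7 percentage points at n=15, or 1/30 = 3.3 points at n=30. These are planned sizes; the efficacy evaluable set may differ.

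**The case against.** The strongest case on the other side is that this is a narrow edge case.

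- **Eligibility.** A patient who stopped a drug for toxicity while still responding is hard to fit in. Inclusion 13 also requires adverse events to have resolved or stabilised, and inclusion 10 requires acute events from prior therapy to be at Grade 1 or lower, or at baseline (alopecia and neuropathy excepted). Consent and screening must also fit into the remaining days, so the figures in the table are upper limits.
- **Timing.** The first on-study scan is at Cycle 4 Day 1, which is 3 × 21 = 63 days after first dose. Shrinkage from the old drug would have to last nine weeks, and longer if confirmation is applied.
- **Direction.** An early scan also misses growth before first dose, which makes response harder to reach.
- **Visibility.** Footnote b to Table 2 collects the best response to the last prior therapy, and SAP 6.6 lists prior systemic therapies by subject.

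All of this stands, and it lowers the likely frequency. It does not remove the permission, and a listing of therapies does not by itself set their end dates against the scan dates.

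A reader might go further and infer that the gap inflates ORR and could wrongly trigger the next stage. The documents do not support that. At an assumed true ORR of 10%, the chance of 3 or more responses in 15 is 0.184. It rises to 0.415, the chance of 2 or more in the other 14, only if one carried-over responder is taken as certain. With an assumed 2% carry-over chance per non-responder, the rate becomes 0.10 + 0.90 × 0.02 = 0.118 and the probability 0.257. No document supplies such a rate. The triggers are also discretionary: the extra cohort may be opened only after other data are reviewed, and Part 2 needs regulatory agreement. SAP 4.1 records that Part 2 was not initiated because responses were too few.

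**Conclusion.** The point holds as a gap between two eligibility and assessment rules. They permit the baseline scan to precede the last prior dose for agents with a half-life under 5.6 days outside the two longer washouts, and neither document prevents change from that drug entering the primary ORR. The size is 6.7 points of ORR per misattributed response at n=15, or 3.3 at n=30. The 25.5 to 13 days of possible overlap rest on assumed half-lives of 0.5 to 3 days.

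Frequency is unknown and probably low, since most entrants will have progressed on earlier treatment. Net direction cannot be determined from the documents. With Part 2 not initiated, the remaining stake is the reported ORR, its interval and how each response is attributed. That justifies a small analysis step now and a scan-order rule if enrolment continues. It is not evidence that the result is biased.

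**What to change.** **In SAP section 8.** Derive a flag for every subject whose last dose of prior systemic therapy falls after the baseline scan, and list flagged subjects with both dates. Add one sensitivity line to the SAP 8.3 summary: ORR with its Clopper-Pearson interval, counting flagged responders as non-responders and keeping the denominator unchanged. The line tests only for inflation; the listing shows how many subjects could be affected in either direction. Protocol 6.8 already calls for all therapies for the primary diagnosis to be recorded whenever taken, and scan dates come with the tumour assessments. How a partial end date is handled should be stated.

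**For any further enrolment.** Reconcile inclusion 13 with footnote u by adding to footnote u and Appendix 1 that the baseline scan is acquired on or after the last dose of prior systemic anti-cancer therapy, and that a pre-consent scan is usable only if no such therapy was given after it. This brings the dosing overlap to zero for every half-life and leaves the washout length as it is. It does not remove any effect of the old drug that lingers after its last dose.

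**Cost.** One derived flag, a short listing and one table line. A few patients would be scanned later in the existing 28-day window instead of relying on an older scan.
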